9.0 TREATMENT PLAN

9.1 Agent Administration

Treatment will be administered on an outpatient basis as per Section 5.0, Figure 2. The patients on study will procure the enzalutamide as stated above through their standard outpatient pharmacy, but will not take any doses of therapy until instructed to do so, and at doses specified by study nurse and investigator. Study drug administration calendars will be filled out by the patient while on study. The patients' pill bottles will be brought to each study visit for pill counting by the research nurse to validate the calendars.

No investigational or commercial agents or therapies other than those described below may be administered with the intent to treat the patient's malignancy with the exception of patients who are chemically castrated who should continue to receive their LHRH agonist/antagonist while on this clinical trial. Medications for bone health (e.g. zoledronic acid or denosumab) should likewise be continued (Section 3.1).

9.2 Management of Castration Related Symptoms:

Treatment with androgens, estrogens, and progestin to control hot flushes is not allowed. However, selective serotonin re-uptake inhibitors (SSRIs) are permitted for the management of hot flashes.

9.3 Dose-Reduction Procedure for Adverse Event Management

In the event where dose-reduction is used for AE management, dose reductions are allowed according to table 2 below, however given the study design, the starting dose for a subject may vary. For mifepristone the dose reduction algorithm is downward from level 1 → 1' → 0 → -1; for enzalutamide dose reductions follow A' → A → B → C depending on subjects starting dose. The maximum time a patient's study medication may be held due to toxicity is 28 days. After which, the patient must be discontinued from study participation. A dose delay of 14 days or more will mandate a dose reduction.

All grade 3 or 4 toxicity (CTCAE 4.0, <http://evs.nci.nih.gov/ftp1/CTCAE/About.html>) that are potentially related to the therapy, unless specifically addressed below, should necessitate holding offending study drug, which can be reintroduced according to the instructions listed below. Holding or reducing dose otherwise (unless specifically addressed below) is at the discretion of the investigator.

- If Grade 1-2 toxicities, give supportive care per institutional guidelines. No study treatment dose reduction.
- If Grade 3 or higher toxicities including headache (interferes with ADL), nausea (TPN, IVF), vomiting (>6 episodes/24hrs, TP or IVF), diarrhea (IVF, hospitalization, hemodynamic collapse), or any other toxicity judged to be related to study treatment is observed where the patient's safety is jeopardized, hold study treatment.

- When toxicity resolves to \leq Grade 1, resume study treatment at full dose.
- If toxicity recurs, hold study treatment, and adjust or add medications to mitigate the toxicity. When resolved to \leq Grade 1, resume study treatment with the first dose level reduction.
- If toxicity recurs, hold study treatment, and adjust or add medications to mitigate the toxicity. When resolved to \leq Grade 1, resume study treatment with these dose level.
- If toxicity recurs despite aggressive medical management, and two dose level reductions, discontinue study treatment.

Several of the potential adverse events for this study are side effects common to both mifepristone and enzalutamide, such as diarrhea, anhedonia, nausea and fatigue. Given the established efficacy of enzalutamide for patients with CRPC, if dose delays or adjustments necessary for non-specific adverse events, it is recommended that the mifepristone be delayed/reduced first, and if no improvement in adverse event with adjustment of mifepristone, enzalutamide then be delayed/reduced.

Table 2. Dose reduction levels

Mifepristone		Enzalutamide	
Level	Dose/Day	Level	Dose
-1	Will be removed from study for toxicity	A'	80 mg/day
0	300 mg/ every other day	A	40 mg/ day
1'	300/600 alternating every other day	B	40 mg every other day
1	600 mg/day	C	40 mg every 3 rd day

[Rest of Page Intentionally Left Blank for Formatting Purposes]

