9.4 Treatment Management of Hypertension

Hypertension may develop while on mifepristone due to excess mineralocorticoid activity due to treatment dependent increase in ACTH. Because of this, hypertension occurring secondary to mifepristone may be most effectively prevented through the concurrent administration of eplerenone which is capable of inhibiting mineralocorticoid induced hypertension. The following table provides a recommended algorithm for treatment-emergent hypertension management. Decisions to hold or decrease the dose of study treatment must be based on blood pressure (BP) readings confirmed with a second measurement at least 5 minutes after the first measurement.

BP Measurements – Systolic/Diastolic	Treatment/Dose Modification
> 140 mm Hg (systolic) and <160 mm Hg OR > 90 mm Hg (diastolic) and < 105 mm Hg OR	
• Add new or additional antihypertensive medications or increase dose of existing medications.• Maintain dose of study treatment.
≥ 160 mm Hg (systolic) OR ≥ 105 mm Hg (diastolic)	
• Hold mifepristone.• Add new or additional anti-hypertensive medications or increase dose of existing medications.• Monitor subject closely for hypotension (if on anti-hypertensive medications) until study treatment is restarted.• Resume treatment at same dose level when BP falls to < 140/90 mm Hg.

If toxicity occurs, hold study treatment, adjust or add medications to mitigate the toxicity. When resolved to \leq Grade 1, resume study treatment with first dose level reduction.

If toxicity recurs at the first dose level reduction, hold study treatment, adjust or add medications to mitigate the toxicity. When resolved to \leq Grade 1, resume study treatment with the second dose level reduction.

[Rest of Page Intentionally Left Blank for Formatting Purposes]

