9.7 Management of Elevated Liver Function Tests

Although elevated liver function studies are an uncommon adverse event for both enzalutamide and mifepristone, given the hepatic metabolism of both drugs, potential for increased toxicity is noted.

- If Grade 1 increases in AST, ALB or bilirubin occur (e.g. increase in AST or ALT from ULN to 2.5 XULN; increase in total bilirubin from ULN to 1.5 XULN): The frequency of liver function test monitoring should be increased per Investigator discretion, if the Investigator judges that the laboratory abnormalities are potentially related to study medication. No study treatment dose reduction is required.
- If Grade 2 increases in AST, ALT or bilirubin occur (e.g. increase in AST or ALT to $>2.5-5\text{XULN}$; increase in total bilirubin from $> 1.5-3 \text{ XULN}$): The frequency of liver function test monitoring should be increased to \geq once a week, if the Investigator judges that the laboratory abnormalities are potentially related to study medication. No study treatment dose reduction is required.
- If Grade 3 or higher increases in AST, ALT, or bilirubin occur (e.g. increase in AST or ALT to $>5 \text{ XULN}$; increase in total bilirubin to $> 3 \text{ XULN}$), hold mifepristone and

enzalutamide and all other concomitant medications that are potentially hepatotoxic. Frequent laboratory evaluations (at least once weekly) should be conducted until the liver function tests return to baseline value or Grade 1. When liver function studies do normalize, first reintroduce enzalutamide at one dose reduction. If after 2 weeks of single agent enzalutamide, AST/ALT are still grade 1 or better, mifepristone may be introduced at one dose level reduction.

If Grade 3 or higher increases in AST, ALT, or bilirubin recur after the first dose reduction hold study medication and all other concomitant medications that are potentially hepatotoxic. Frequent laboratory evaluations should be conducted (at minimum weekly) until the liver function tests return to baseline value or Grade 1. Liver enzyme measurements should be made immediately, regardless of when the next study visitor monitoring interval is scheduled.

If study treatment resumption is considered for patients who have experienced Grade 3 increases in AST, ALT, or bilirubin with the first dose reduction, resume study treatment with the second dose level reduction as above when AST, ALT, or bilirubin returns to baseline value or Grade 1.

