If Grade 4 increases in AST, ALT, or bilirubin occur (e.g. increase in AST or ALT to > 20X ULN; increase in total bilirubin to >10 XULN), patients must discontinue study treatment immediately and will not be re-challenged. They should be followed until resolution of abnormal liver function tests.

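### Section 9.4 gives two different restart instructions for a first hypertension hold; the 14-day rule in 9.3 and the Grade 4 liver rule in 9.7 need clarifying alongside it

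*Combined protocol and SAP*

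**What the plan says.** **Hypertension (9.4).** The table, offered as a recommended algorithm, has two rows. In the lower row (above 140 and below 160 systolic, or above 90 and below 105 diastolic) the study dose is maintained. In the upper row (160 or more systolic, or 105 or more diastolic) mifepristone is held, antihypertensives are added or increased, and the instruction is "Resume treatment at same dose level when BP falls to < 140/90 mm Hg". Two sentences follow the table. The first covers toxicity that *occurs*: study treatment is held and, at Grade 1 or below, the site is to "resume study treatment with first dose level reduction". The second covers toxicity that *recurs* at that first reduction, and leads to the second reduction.

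**General rule (9.3).** On the length of a hold: "The maximum time a patient's study medication may be held due to toxicity is 28 days", after which the patient comes off study. Also: "A dose delay of 14 days or more will mandate a dose reduction". After a first Grade 3 or higher event that settles to Grade 1 or below, the site is to "resume study treatment at full dose", with no limit stated on how long the hold has lasted. Section 9.5 (first anasarca or pulmonary edema) and Section 9.9 (rash) also restart at full dose without such a limit.

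**Liver tests (9.7).** One rule begins "If Grade 3 or higher increases in AST, ALT, or bilirubin occur". It holds both drugs and, after normalization, brings back enzalutamide and then possibly mifepristone, each one level lower. A later rule says that with Grade 4 increases "patients must discontinue study treatment immediately and will not be re-challenged".

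**The concern.** A restart rule should give one answer for one event. In 9.4 a site meeting a first hold-level blood pressure finds two answers a few lines apart, and following either one departs from the other. The trial is multi-site. Protocol deviations must be reported (10.6), and 20% of charts are audited each year for, among other things, administration of treatment (10.8.4). Neither a site nor an auditor could say which action complies.

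At stake are the patient's dose after a safety hold and consistent handling across sites. In phase II the mifepristone rules act only on the combination arm, so inconsistent handling would fall on that arm's exposure. In phase I the dose decision uses the ratio of day 57 to day 29 enzalutamide-plus-metabolite troughs (5.1.1.1). Whether mifepristone alone or both drugs were held in that window could affect a patient's day 57 value.

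**Working it through.** The plan gives no figure to reproduce, and no arithmetic applies. The check sets each restart instruction against the others that share its trigger.

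**Step 1. First hypertension event at the hold threshold (9.4).**

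| Element | Table, upper row | Text beneath the table |
|---|---|---|
| Trigger | 160 or more systolic, or 105 or more diastolic | Toxicity *occurs*; no threshold given |
| What is held | Mifepristone | Study treatment |
| Recovery criterion | Below 140/90 mm Hg | Grade 1 or below |
| Restart dose | Same level | First reduction |

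The restart doses cannot both be followed, and the conflict does not depend on hold length. Section 9.4 does not say what blood pressure corresponds to Grade 1, so the text does not show whether the two recovery criteria coincide.

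**Step 2. The 14-day sentence (9.3), by hold length.**

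- Under 14 days: the sentence does not apply, so there is no conflict.
- 14 to 28 days: the sentence requires a reduction. It meets a full- or same-dose restart only for first events in 9.3, the 9.4 table row, first anasarca or pulmonary edema in 9.5, and rash in 9.9.
- Over 28 days: the patient is off study, so no restart question arises.

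Several long holds raise no such tension. Restart after a first recurrence in 9.3 and after a recurrence in 9.5 is already at a reduced level, and so is restart after liver holds in 9.7. Grade 4 hypokalemia in 9.6 is referred to the study PI.

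Section 9.3 twice makes an exception for matters dealt with later in Section 9: once for the rule on holding drug at Grade 3 or 4, and once for investigator discretion. Neither exception is attached to the 14-day sentence, so precedence between that sentence and the event-specific restart dose is not settled.

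**Step 3. Liver tests (9.7).** The first rule starts at AST/ALT above 5 x ULN or bilirubin above 3 x ULN and has no upper bound. The Grade 4 rule starts at above 20 x ULN or above 10 x ULN. Because 20 exceeds 5 and 10 exceeds 3, every Grade 4 value also meets the first rule as written. Below the Grade 4 thresholds only the first rule applies. After a recurrence, 9.7 contemplates resumption only for patients with Grade 3 increases, which suggests that Grade 4 was meant to be separate.

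**The case against.** **On 9.4**, the best defense is that *occurs* is a slip for *recurs*. Sections 9.3 and 9.5 both run from full dose to first reduction to second reduction, and that one word would give 9.4 the same sequence. It would also supply an instruction for recurrence at the original dose, which 9.4 otherwise lacks. The table itself speaks of study treatment being restarted after mifepristone is held, so the difference in what is held may be loose wording. This is plausible, but the text does not say it, and it would leave the two recovery criteria unreconciled. That the table is only a recommendation does not tell a site which text to follow.

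**On the 14-day sentence**, its mandatory wording can be read as overriding a default: under 14 days the event rule, 14 to 28 days a reduction, beyond that off study. That reading is coherent. What remains is that the protocol does not state it.

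**On liver tests**, the Grade 4 rule is specific, comes last, has its own thresholds and is absolute. It would have no purpose unless it removed Grade 4 from the general rule. This largely stands: the overlap is loose drafting.

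A reader might infer that all three passages give opposite instructions, and that every patient held 14 to 28 days and every Grade 4 liver event is affected. The documents do not support that. Many long holds already restart at a reduced level, and rechallenge after Grade 4 would mean disregarding an explicit prohibition.

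**Conclusion.** The contradiction in 9.4 stands as printed: one first event, two restart doses, with a different held drug and a different recovery criterion. It reaches first hypertension events at the hold threshold. The 14-day and Grade 4 liver points are secondary clarifications.

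The number of patients affected cannot be derived, because the documents give no expected rate of hold-level hypertension or of long holds. A reader might go further and infer that the toxicity comparison or the PSA endpoint is biased. The documents contain no figure that shows this, and no stated sample size, power or alpha is affected. The effects on exposure and on the phase I trough ratio are possible consequences, not demonstrated ones.

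The conclusion assumes that the sentences under the 9.4 table concern hypertension, since they stand in that section and name no other toxicity. It takes no view on which restart rule is clinically right.

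**What to change.** - **9.4:** reconcile the table and the text beneath it into one instruction for each occurrence (first, second, later), stating which drug is held, which recovery criterion applies and the restart level.
- **9.3:** state whether the 14-day sentence or the event-specific restart governs a hold of 14 to 28 days, and cross-refer from 9.4, 9.5 and 9.9.
- **9.7:** reword the Grade 3 or higher rule and the Grade 4 rule so that they no longer overlap.

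The choice of rule in each case belongs to the sponsor's clinicians. The cost is protocol wording in Section 9, communicated to sites. No data collection, analysis or sample size changes.

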9.6 Management of Hypokalemia

Hypokalemia may occur in patients treated with mifepristone due to mineralocorticoid excess and potentially. Initial management of hypokalemia should include oral K⁺ supplementation as well as the addition of eplerenone, as appropriate.

Serum K ⁺	Grade	Action	Further Action and/or Maintenance
<3.5mM-3.0mM	Grade 1	Initiate oral K ⁺ Supplements	Titrate K ⁺ dose to maintain serum K ⁺ $\geq 3.5\text{mM} \leq 5.0\text{mM}$ (Maintenance of pts at $\geq 4.0\text{mM}$ is recommended); weekly laboratory studies until K ⁺ $\geq 3.5\text{mM} \leq 5.0\text{mM}$.
<3.0mM-2.5mM	Grade 3	Withhold mifepristone and initiate IV K ⁺ and cardiac monitoring	Restart mifepristone at dose level -1; Titrate K ⁺ dose to maintain serum K ⁺ $\geq 3.5\text{mM} \leq 5.0\text{mM}$; weekly laboratory studies until K ⁺ $\geq 3.5\text{mM} \leq 5.0\text{mM}$.
<2.5mM	Grade 4	Withhold mifepristone and initiate IV K ⁺ and cardiac monitoring	Call study PI prior to re- initiating study treatment.

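### Section 9.3 returns a first related Grade 3 or higher seizure to the full assigned dose by default after a hold of under 14 days, and no visible rule requires a safer restart

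*Combined protocol and SAP*

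**What the plan says.** **The general ladder (9.3).** A potentially related Grade 3 or 4 toxicity with no rule of its own leads to a hold of the offending drug, "which can be reintroduced according to the instructions listed below". The hold step names headache, nausea, vomiting and diarrhoea, and then "any other toxicity judged to be related to study treatment" where safety is at risk. After the first event the instruction, once toxicity is down to at most that level, is "Grade 1, resume study treatment at full dose". The first dose-level reduction comes if the toxicity recurs. Two time limits apply: "A dose delay of 14 days or more will mandate a dose reduction", and a hold beyond 28 days ends participation. Other holds and reductions are left to the investigator.

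**Specific rules (9.4 to 9.9).** These cover hypertension, edema, hypokalemia, liver tests, adrenal insufficiency and rash. None covers seizure. After a Grade 3 liver-test rise, 9.7 says to "first reintroduce enzalutamide at one dose reduction". After Grade 4, "patients must discontinue study treatment immediately and will not be re-challenged".

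**Seizure elsewhere.** It appears as a 0.6% incidence on enzalutamide (1.4), as a risk that rises with plasma concentration (1.5), as one potentially related event on mifepristone (1.8), as an entry exclusion (3.2), in the reasoning for the DLT window (5.2) and, as convulsions, among the examples of important medical events (10.2). None of these sets a dosing action.

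**Exposure.** Section 5.1.1.1 estimates a 4-fold rise in enzalutamide exposure with mifepristone, starts enzalutamide at a quarter of the standard dose, and accepts a recommended dose with a cohort-mean trough ratio of up to 1.5.

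**The concern.** The protocol treats seizure as an exposure-related hazard of enzalutamide, and the trial adds a drug expected to slow enzalutamide metabolism. The written default nevertheless restores the same assigned dose after the first event, and the ladder first requires a reduction after a second seizure.

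Resolution to Grade 1 or lower is also a weak condition for an episodic event. Blood pressure, edema and liver tests can be followed down to a safe value. A patient who is no longer convulsing has not thereby shown that the exposure has changed. On recurrence, 9.3 says to adjust or add medication, but for seizure that step is constrained: anticonvulsant use bars entry (3.2), and carbamazepine and phenytoin are prohibited (9.12).

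What is at stake is the safety of an individual patient. The primary analysis is not affected.

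**Working it through.** **1. Rule trace.** The plan gives no figure to reproduce, so the rules are set side by side.

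| Event | Governing text | Restart |
|---|---|---|
| First related Grade 3+ seizure, resolved, hold under 14 days | 9.3 ladder | Full assigned dose |
| Same, hold of 14 to 28 days | 9.3 | Reduction mandatory |
| Same, hold over 28 days | 9.3 | Off study |
| Recurrent seizure | 9.3 ladder | First reduction |
| First Grade 3 liver-test rise | 9.7 | Enzalutamide one level down; mifepristone one level down after 2 weeks |
| Grade 4 liver-test rise | 9.7 | None |
| Anasarca or pulmonary edema needing oxygen, first event | 9.5 | Full dose |
| Blood pressure at or above 160 systolic or 105 diastolic | 9.4 table | Same dose level (the text under the table points to a reduction) |
| Severe rash | 9.9 | Full-dose mifepristone |

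Full dose here means the assigned dose, which at the start of phase I is 40 mg/day enzalutamide in combination.

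**2. What a restart does to exposure.** Inputs: half-life 5.8 days (1.5); hold h = 7 days (assumed); linear kinetics with unchanged clearance (assumed).

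- Fraction left after the hold: r = 0.5^(h/t½) = 0.5^(7/5.8) = 0.433. A 13-day hold gives 0.211.
- Level 28 days after restart, relative to the pre-event steady state: f + (r − f) × 0.5^(28/t½), where f is the restart dose as a fraction of the old dose and 0.5^(28/5.8) = 0.035.
- Full dose, f = 1: 1 − 0.567 × 0.035 = 0.980.
- One level down, f = 0.5 (80 to 40 mg/day, or 40 mg/day to 40 mg every other day): 0.5 − 0.067 × 0.035 = 0.498.

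Sensitivity: suppose the 4-fold rise were entirely reduced clearance and lasted throughout, so t½ = 4 × 5.8 = 23.2 days. Then r = 0.811, and the 28-day levels are 0.918 and 0.635. This is an upper bound on what remains. If mifepristone is held too, only about 1% (24-hour half-life) to 32% (90% eliminated in 2 weeks) of it is left after 7 days, going by 1.8.1.

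**3. How often.** Combination patients: 24 (estimated, phase I) + 42 (phase II) = 66.

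- At 0.6% (1.4): expected seizures 66 × 0.006 = 0.40; chance of at least one 1 − 0.994^66 = 33%.
- At 1/41 (1.8, Alzheimer's patients on 300 mg/day): 66/41 = 1.6; chance 1 − (40/41)^66 = 80%.

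Both count any seizure. The full-dose step is reached only by a first event that is related, Grade 3 or higher, resolved, held under 14 days and then restarted. The documents give no basis for that smaller figure.

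**4. What the 1.5 limit allows.** 1.5 × 160 = 240 mg/day equivalent under the dose proportionality in 1.5. Section 1.4 names 240 mg/day as the maximum tolerated dose. The limit is on a cohort mean, so individual patients can lie above it.

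**The case against.** **Full dose after a first serious event is the protocol's usual pattern.** This stands. A reader might infer from the liver rule that seizure has been singled out for lenient handling. Sections 9.4, 9.5 and 9.9 do not support that, and 9.7 gives hepatic metabolism of both drugs as its reason for being stricter. Hypokalemia is not a clean comparator either: 9.6 says "Restart mifepristone at dose level -1", which is 300 mg every other day in Table 1 but removal from study in Table 2.

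**Nobody is forced to restart.** This also stands. The wording in 9.3 is permissive. Section 6 ends therapy for unacceptable toxicity or at the investigator's decision. Serious events are reported promptly (10.5, 10.6) and reviewed weekly (10.8.4), and the independent monitor sees all of them and can remove a patient (10.8.5). So it would be wrong to read 9.3 as compelling a full-dose restart. But none of these provisions requires a lower dose or a stop, and in a multisite trial the written default matters.

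**Exposure is controlled.** A reader might take the 4-fold estimate to mean 4-fold exposure. It does not: the starting dose is quartered to offset it, and the ratio limit follows. What remains is the permitted mean of up to 1.5 and variation between patients.

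**The event is rare.** True. The 98% figure says only that full dose restores full exposure; it is not a recurrence risk. The 33% and 80% must not be read as the chance of a full-dose restart after seizure.

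**Low-grade seizures and the DLT count.** A reader might go on to infer that a mild seizure escapes action, since 9.3 says "If Grade 1-2 toxicities, give supportive care per institutional guidelines. No study treatment dose reduction", and that cohort decisions suffer. That depends on a grading table not in the documents. Even if every seizure at 0.6% fell below Grade 3 within the window, the chance of at least 4 DLTs in 12 would move only from 20.5% to 21.8% at an assumed 20% rate of other DLTs. No change to 5.2 is warranted.

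**Conclusion.** The point holds for a first potentially related Grade 3 or higher seizure that resolves to Grade 1 or lower within a hold of under 14 days. For that case the protocol's default is the full assigned dose, and the protocol's own account of enzalutamide and seizure argues against it. Existing oversight makes a safer choice possible without requiring one.

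The practical size is small: about 0.4 seizures of any kind among 66 combination patients at the enzalutamide rate, and 1.6 at a rate borrowed from one event in another population. For a patient who is affected, the choice is between about 98% and about 50% of the pre-event exposure four weeks after restart (92% and 64% in the slow-clearance case). These figures assume linear kinetics and a 7-day hold of enzalutamide.

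Figure 3 is not shown, so a seizure rule there cannot be excluded. This is a cheap improvement on patient-safety grounds. It does not show that the protocol is unsafe overall, nor does it fault the analysis.

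**What to change.** Add one paragraph to 9.3:

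> The full-dose resumption step does not apply to a potentially related seizure. Hold all study drug. Discontinue study treatment unless the study chair and the independent monitor agree to a restart beforehand. Any restart is at a reduced enzalutamide dose (80 mg/day for a patient on 160 mg/day, otherwise the next lower level in Table 2) and a reduced mifepristone dose. If no lower level exists for a drug (enzalutamide level C, or the lowest permitted mifepristone level), that drug is not restarted.

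The 160 mg/day case has to be spelled out because Table 2 starts at 80 mg/day. The last sentence is needed because nothing lies below level C and because Tables 1 and 2 disagree on mifepristone level −1. The sponsor should settle that disagreement in the same amendment, and should say that the paragraph takes precedence over the rest of the ladder.

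**Cost.** No extra visits or tests. There is a review step before any restart, and lower enzalutamide exposure or loss of study treatment for about one patient. Section 1.5 says enzalutamide may be less effective at lower levels. If mifepristone stays off, its effect on enzalutamide clearance also fades, so exposure falls for two reasons; the study chair and monitor should weigh that before agreeing to a restart.

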5.1.1 Phase I Study Drug Administration

- The eligible subjects will begin standard of care dosing of enzalutamide at 160mg/day.
- Beginning day 29, subjects will enter phase I combination drug portion of the study beginning at mifepristone dose 0 and at enzalutamide dose A (40mg/day). Dose levels are defined in Table 1.
- After the first 6 patients are evaluated at this dose level, subsequent patients will be enrolled and dosed similarly (after 28 day standard dose lead in) with dose of enzalutamide and mifepristone to be determined based on the following dose escalation/de-escalation rules.

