5.1.1.1 Phase I Dose Level Determination

Mifepristone and enzalutamide dose levels (Table 1) will be adjusted by dose cohorts according to the following rules, which are illustrated in the algorithm below (Figure 3). Each cohort will enroll a minimum of six patients, beginning with dose level 0A, with additional patients added or doses adjusted as described in the algorithm by following rules 1-4 in order to take into account dose limiting toxicity (DLT) rate and the change in steady-state (C_{trough}) enzalutamide levels (†, Figure 3). As noted above, it is estimated that mifepristone at both 300mg and 600mg will increase enzalutamide exposure by approximately 4-fold, with no significant difference in CYP inhibition based on mifepristone

dose. Thus, the initial dose level for enzalutamide, to ensure safety is $\frac{1}{4}$ the standard dose of 160mg/day. As noted in the Figure 3 rules, if enzalutamide plasma levels are lower then expected, the enzalutamide dose will be increased for the next cohort (e.g. from A to A'), whereas if higher then anticipated, the dose will be decreased (e.g. from A to B).

[figure not shown]
Mifepristone dose will be escalated or decreased based on tolerability (DLT rate-see proceeding section). **The recommended Phase II dose (RP2D) will be the highest mifepristone dose in combination with enzalutamide such that <33% (4/12) experience DLT and $\checkmark \leq 1.5$.** Although we anticipate that a 12 patient cohort will be sufficient to estimate effect of mifepristone on enzalutamide clearance and that the intra-patient comparison will account for variability within each patient in baseline enzalutamide clearance characteristics, it is possible that the variability in affect of mifepristone on enzalutamide metabolism will be larger then anticipated. In this case, dose cohorts will be expanded in a protocol amendment to better characterize PK interactions.

Table 1. Dose levels

Mifepristone		Enzalutamide	
Level	Dose	Level	Dose
-1	300 mg/every other day	A'	80 mg/day
0	300 mg/day	A	40 mg/ day
1	600 mg/day	B	40 mg every other day
		C	40 mg every 3 rd day

[Rest of Page Intentionally Left Blank for Formatting Purposes]

Figure 3. Phase I schema and dose escalation/de-escalation algorithm

r_i = ratio of trough drug concentration after 28 days concurrent dosing divided by trough drug concentration after 28 days enzalutamide alone dosing for an individual patient

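### Mifepristone levels 0 and -1 mean different doses in Table 1 and Table 2, and Table 2, which governs reductions, has no row for the 300 mg/day starting dose

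*Combined protocol and SAP*

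**What the plan says.** Table 1 (5.1.1.1) defines the phase I mifepristone levels. Level -1 is "300 mg/every other day", level 0 is 300 mg/day and level 1 is 600 mg/day. Section 5.1.1 points to this table and starts combination dosing at level 0. Section 5.1.1.1 adds: "Each cohort will enroll a minimum of six patients, beginning with dose level 0A". Section 1.9 gives that start in mg, as 300 mg/day of mifepristone.

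For adverse events, 9.3 states that "dose reductions are allowed according to table 2 below". Table 2 lists level 1 as 600 mg/day, level 1' as "300/600 alternating every other day", level 0 as "300 mg/ every other day" and level -1 as "Will be removed from study for toxicity". The order of steps is also given in 9.3: "For mifepristone the dose reduction algorithm is downward from level 1" through 1' and 0 to -1. The same section makes a reduction compulsory once dosing has been delayed for at least 14 days.

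The grade 3 row of the hypokalaemia table in 9.6 tells sites to resume mifepristone at level -1 and names no table. The grade 4 row allows treatment to resume after a call to the study PI. Sections 9.3, 9.4, 9.5 and 9.7 each refer to a second dose-level reduction.

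**The concern.** These are operative safety instructions, and the labels are what link them. Section 4.2 gives the site a dose level at registration, and that level comes from Table 1. When toxicity occurs, the site is sent to a table in which two of the same labels mean something else and in which the phase I starting dose does not appear. The same event could then keep one patient on a reduced dose and take another off study, depending on whether the site follows the label or the milligrams.

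What is at stake is consistent handling of toxicity across sites. No statistical quantity depends on it.

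**Working it through.** There is no figure in the plan to reproduce. The check sets the two tables side by side and converts each entry to an average daily dose. Inputs are Table 1 (5.1.1.1), Table 2 and the reduction order (9.3), and the grade 3 row of 9.6.

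Conversions: 300 mg every other day = 300 / 2 = 150 mg/day. Alternating 300 and 600 mg = (300 + 600) / 2 = 450 mg/day.

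| Level | Table 1 | Table 2 | Agree? |
|---|---|---|---|
| 1 | 600 mg/day | 600 mg/day | yes |
| 1' | not listed | 450 mg/day average | n/a |
| 0 | 300 mg/day | 150 mg/day average | no |
| -1 | 150 mg/day average | removal | no |

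Three labels appear in both tables (1, 0, -1), and two of them differ. The dose of 300 mg/day appears only in Table 1. The enzalutamide halves of the two tables agree at every level, so the conflict is confined to mifepristone. The order in 9.3 has four levels and Table 2 has four rows, so no row appears to have dropped out.

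**Reduction from 300 mg/day.**
- By label: 0 to -1 in Table 2, which is removal.
- By dose: the next lower dose listed in Table 2 is 300 mg every other day, a cut of 1 - 150/300 = 50%.

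**Grade 3 hypokalaemia (9.6, level -1).**
- Table 1 meaning: 300 mg every other day. From 600 mg/day the cut is 1 - 150/600 = 75%, and from 300 mg/day it is 50%. For a patient already on 300 mg every other day it is 1 - 150/150 = 0, so there is no reduction.
- Table 2 meaning: resume at a level defined as removal, which contradicts itself. It would also make grade 3 stricter than grade 4.

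**Lower mifepristone doses available.**
- From 600 mg/day: two in either table (Table 1: 300 mg/day and 300 mg every other day; Table 2: alternating and 300 mg every other day).
- From 300 mg/day: one in either table (300 mg every other day). A second reduction for such a patient could come only from enzalutamide, where the text speaks of study treatment as a whole.

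**Effect of carrying Table 1 labels into the 9.3 order.**
- Steps from 600 mg/day now: 600, then 450, then 150 mg/day on average.
- With the Table 1 meaning of level 0: 600, then 450, then 300 mg/day. The second step would be 300 / 150 = 2 times the present dose.

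**The case against.** The strongest reply is that a careful reader can resolve most of this, and much of that reply stands.

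- A reader might infer that 9.6 takes patients with grade 3 hypokalaemia off study, or that it cannot be carried out. The text does not support this. An instruction to resume a drug cannot mean removal, and the Table 1 meaning works. What remains is that 9.6 uses a label in a sense that the governing reduction table contradicts, and that it gives no reduction to a patient already at that dose.
- A reader might infer that patients on 300 mg/day will be removed at their first reduction. A site would have to carry the label 0 across and ignore the dose printed beside it in Table 2. Section 9.3 also warns that starting doses may differ, and under 4.1 the assigned dose is sent to the site as well as the level. Reading by dose is more natural, but the plan does not say to do so.
- A reader might infer that the references to a second reduction are void for these patients. Most of that wording concerns study treatment, which includes enzalutamide. Section 9.3 reduces mifepristone first and enzalutamide next for non-specific events, and enzalutamide has lower steps of its own.
- Reductions may be uncommon. In 9.3, in 9.5 and in the 9.4 table, the first event resumes at full or unchanged dose unless the hold reaches 14 days. Section 1.8 reports no high-grade hypokalaemia in the cited 300 mg/day study. The weekly safety meetings and phase I teleconferences in 10.8.4 give sites a route to clarification.

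None of this removes the clash of labels or supplies the missing row.

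**Conclusion.** The plan is wrong as written on the labels, and this should be fixed. Levels 0 and -1 carry different meanings in the two tables, the governing reduction table omits the phase I starting dose, and 9.6 agrees with Table 1 but not with Table 2.

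At least 6 phase I patients (the first cohort) are planned at 300 mg/day. If the RP2D is 300 mg/day, up to 42 patients in the phase II combination arm would be affected. If it is 600 mg/day, the missing starting row does not affect phase II. How many patients would need a reduction, or would meet the grade 3 row of 9.6, cannot be derived from the documents.

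Confidence is high for the mismatch itself. That sites would in fact diverge is a possibility, not a demonstrated result. A reader might also infer damage to the primary comparison through avoidable withdrawals. The documents give no basis for that, and no effect on endpoint, power or sample size is claimed.

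**What to change.** Keep every current dose and change only how it is identified.

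1. In Table 2 and the 9.3 order, use labels that do not clash with Table 1, or state the steps in mg: 600 mg/day, then 300/600 mg alternating, then 300 mg every other day, then removal.
2. Add a 300 mg/day entry whose next step is 300 mg every other day, followed by removal.
3. In the grade 3 row of 9.6, give the restart dose in mg (300 mg every other day), and say what to do for a patient already on it.
4. State that patients starting at 300 mg/day have one mifepristone reduction.

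Do not simply copy the Table 1 labels into the 9.3 order. That would raise the second step from 600 mg/day from 300 mg every other day to 300 mg/day, which is a change of dose after repeated toxicity and not a change of wording.

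The cost is a short protocol amendment, plus one clinical decision by the investigators for item 3. No analysis or sample size text needs to change.
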